**Table 14: Phase 2 — Blood Sampling for Pharmacokinetic, Pharmacodynamic, Genetic, and Other Assessments**

Visit or Cycle	Day	For PK (see NOTE)	Additional Time Points for Rich PK Subset	For ADA	For PBMC	For [REDACTED]	For PGx
Screening	—	—	—	—	—	—	X 
Cycle 1	1	Predose  30 min ( $\pm$ 15 min) 	—	Predose 	Predose 	Predose 	—
	2	—	24 h ( $\pm$ 60 min) 	—	—	—	—
	8	—	168 h ( $\pm$ 4 h) 	—	—	—	—
Cycle 2	1	Predose 	—	Predose 	Predose 	Predose 	—
Cycle 3	1	Predose 	—	Predose 	Predose 	—	—
Cycle 4	1	Predose  30 min ( $\pm$ 15 min) 	—	Predose 	Predose 	Predose 	—
	2	—	24 h ( $\pm$ 60 min) 	—	—	—	—
	8	—	168 h ( $\pm$ 4 h) 	—	—	—	—
Cycles 5, 6, 12, 18, 24	1	—	—	Predose 	—	—	—
Discontinuation	—	X	—	X	X	X	—
Safety Follow-up Visit	4 wk after last dose	X	—	X	—	—	—
Follow-up Visit	3 mo after last dose	X	—	X	—	—	—

Abbreviations: ADA: antidrug antibody; [REDACTED] DNA: deoxyribonucleic acid; h: hour(s); mo: month; min: minute(s); PBMC: peripheral blood mononuclear cell; PGx: pharmacogenomics(s); PK: pharmacokinetic(s); wk: week(s).

 Blood sample for PGx is collected only if an ‘optional’ PGx consent is signed.

 Predose samples will be collected within 30 minutes before starting the AGEN2034 infusion.

 Blood samples collected on Day 1 at 30 ( $\pm$  15) minutes after the **end** of infusion

 As of Amendment 5 (27 September 2019), additional rich PK sampling will be collected in a subset of approximately 20 subjects in selected sites. Rich PK sampling will occur on Days 2 and 8 of Cycles 1 and 4 at 24 hours ( $\pm$  60 min) and 168 ( $\pm$  4) hours, respectively, after the **start** of the infusion.

**NOTE:** It is important to record all infusion start dates/times, infusion end dates/times, infusion interruption(s) start and end dates/times, infusion flush end dates/times, and blood sample dates/times completely and accurately (to the nearest minute). Blood for the 30-minute postdose PK samples should **never** be taken during the infusion and should be drawn at least 15 min after the end of infusion.

## **6.3. Visit Requirements**

### **6.3.1. Screening**

Visit requirements are outlined for Phase 1 in [Section 6.1](#) and for Phase 2 in [Section 6.2](#). Specific procedure-related details are provided in [Section 6.4](#).

### **6.3.2. Treatment Phase**

Visit requirements are outlined for Phase 1 in [Section 6.1](#) and for Phase 2 in [Section 6.2](#). Specific procedure-related details are provided in [Section 6.4](#).

Subject should continue to receive all assessments as defined in the Treatment phase of the Schedule of Assessments while they are actively receiving treatment.

### **6.3.3. End-of-Treatment Visits**

Visit requirements are outlined for Phase 1 in [Section 6.1](#) and for Phase 2 in [Section 6.2](#). Specific procedure-related details are provided in [Section 6.4](#).

#### **6.3.3.1. Discontinuation Visit**

The Discontinuation Visit should occur at the time study drug is discontinued for any reason. If the Discontinuation Visit occurs 4 weeks from the last dose of study drug, at the time of the mandatory Safety Follow up Visit, procedures do not need to be repeated. Procedures at the time of discontinuation are detailed in Section 6.3.3.2, Safety Follow up Visit.

#### **6.3.3.2. Safety Follow-up Visit**

The mandatory Safety Follow-Up Visit should be conducted for all subjects approximately 4 weeks after the last dose of study drug or before the initiation of a new antineoplastic treatment, whichever comes first. Subjects with an AE of Grade >1 will be further followed until the resolution of the AE to Grade 0-1 or until beginning of a new antineoplastic therapy, whichever occurs first. Subjects with an adverse drug reaction (ADR) ongoing at the Safety Follow-up Visit must be followed up until the ADR resolves, becomes stable, or is considered not clinically significant by the investigator.

### **6.3.4. Follow-up Phase**

In Phase 1, subjects who discontinue treatment will be followed for up to 12 months after the last dose of study drug or until death, withdrawal of consent, or becoming lost to follow-up.

In Phase 2, subjects who discontinue treatment will be followed for up to 24 months after the last dose of study drug or until death, withdrawal of consent, or becoming lost to follow-up.

Follow-up visits and survival follow-up requirements are outlined in [Section 6.1](#) and [Section 6.2](#), respectively, for Phase 1 and Phase 2. Specific procedure-related details are provided in [Section 6.4](#).

#### **6.3.4.1. Follow-up Visits**

All subjects who discontinue treatment will have at least one post-treatment visit at 3 months ( $\pm 7$  days) after last dose of study drug.

For both study Phases, subjects who received the maximum administrations of AGEN2034, who have achieved a complete response (CR) according to RECIST 1.1, or who have discontinued treatment due to reasons other than disease progression and/or start of a new line of therapy should be have Follow-up Visits every 3 months for up to 12 months after last dose of study drug (see schedules in [Section 6.1](#)) or until disease progression and/or start of a new line of therapy.

For Phase 2 (see schedule in [Section 6.2](#)), subjects who present with progressive disease and/or start a new line of therapy will move into the Survival Follow-up Phase. Every effort should be made to collect subject information on the start of new antineoplastic therapy, disease progression and death.

#### **6.3.4.2. Survival Follow-up (Phase 2 only)**

There is no survival follow-up for Phase 1.

For subjects in Phase 2, after the first Treatment Follow-up Visit, subjects with progressive disease and/or who start new line of therapy will move into Survival Follow-up. Subjects should be contacted by telephone to assess for survival status every 2 months for up to 12 months after their last dose of study drug.

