Dosage and Administration	
AGEN2034 is an IgG4 antibody designed to block PD-1.
 
Dose Levels
 
Phase 1: Part A1: 1, 3, and 10 mg/kg IV every 2 weeks
 
Part A2: 6 and 10 mg/kg IV every 3 weeks
 
Phase 2: 3 mg/kg IV every 2 weeks
 
Administration
 
AGEN2034 will be administered IV over 60 minutes (-10/+20 min)

Planned Trial Duration	
The maximum trial duration for a subject is estimated to be up to approximately 49 months. This includes a screening period, a planned treatment period of up to approximately 24 months, and a follow-up period of up to 24 months after the last dose of study treatment.
 
The overall trial duration is expected to be approximately 63 months.

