Schedule of Visits and Assessments	
Screening Period (Phase 1 and Phase 2) Screening assessments will be conducted within 42 days prior to first treatment dose, with associated evaluations and procedures.
 
Treatment Phase (Phase 1 and Phase 2) The treatment phase is divided into 2-week (Phases 1 and 2) or 3-week (Phase 1) cycles with associated evaluations and procedures that must be performed at specific time points. Each cycle begins with the administration of AGEN2034. Subjects will be treated for up to 24 months or until disease progression, unacceptable toxicity, or any criterion for stopping the study drug or withdrawal from the trial occurs. Tumor assessments will be conducted every 6 weeks from first dose until disease progression or a new line of therapy is initiated.
 
End-of-Treatment (Phase 1 and Phase 2)
 
Discontinuation Visit and Safety Follow-up Visit: All subjects who discontinue the trial treatment prematurely for an AE should have a full safety evaluation at the time of discontinuation (Discontinuation Visit).
 
A mandatory Safety Follow-up Visit should be scheduled 4 weeks after the last dose of study drug or before the initiation of a new antineoplastic treatment, whichever comes first. Subjects with an AE of Grade > 1 will be further followed until the resolution of the AE to Grade 0-1 or until beginning of a new antineoplastic therapy, whichever occurs first. Subjects with an adverse drug reaction (ADR) ongoing at the Safety Follow-up Visit must be followed up until the ADR resolves, becomes stable, or is considered not clinically significant by the Investigator.
 
Follow-up Phase (Phase 1 and Phase 2) Subjects who discontinue treatment will be followed for up to 12 months (Phase 1) or 24 months (Phase 2) after the last dose of study drug or until death, withdrawal of consent, or becoming lost to follow-up.
 
Follow-up Visits Visits with associated evaluations and procedures will occur every 3 months for up to 12 months following the last dose of study drug or until disease progression and/or start of a new line of therapy. Tumor assessments will continue every 6 weeks from first dose until discontinuation of study drug.
 
Survival Follow-up (Phase 2 only) Subjects in Phase 2 who present with progressive disease and/or start a new line of therapy will be contacted by phone every 2 months to assess for survival for up to 12 months after the last dose of study drug.

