### **3.4. Planned Trial Duration**

The maximum trial duration for a subject is estimated to be up to approximately 49 months. This includes a screening period, a planned treatment period of up to approximately 24 months, and a follow-up period of up to 24 months after the last dose of study drug.

The overall trial duration is expected to be approximately 63 months:

- First subject in: Q2 2017
- Last subject out (after follow-up): Q2 2022

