### **3.5. Definition of End of Trial**

If the trial is not terminated for a reason provided in [Section 4.4.3](#), the end of the trial is defined as 24 months after the last subject has received the last planned dose of study drug.

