Full serum chemistry 	X								X	X	X			
Hematology tests 	X		X	X			X	X	X	X	X			
Coagulation tests 	X			X			X		X	X	X			
Endocrine function tests 	X			X			X		X	X	X			
Urinalysis 	X			X			X		X	X	X			
Serum pregnancy test	X 													
Urine pregnancy test		X 					X		X	X	X			
Study drug administration 														
AGEN2034			X		X		X	X						

Abbreviations: ADA: anti-drug antibody; AEs: Adverse Events; d: day; ECG: electrocardiogram; ECOG: Eastern Cooperative Oncology Group; IERC: Independent Endpoint Review Committee; m: month; PBMC: peripheral blood mononuclear cell; PGx: pharmacogenomics; PK: pharmacokinetics; w: week.

Note: Where applicable, assessments performed prior to treatment unless otherwise indicated.

 All subjects who discontinue treatment will have at least one Follow-up Visit at 3 months (± 7 days) after last dose of study drug. Subjects who discontinue due to disease progression and/or start of a new line of therapy will then end participation in the trial. Subjects who received the maximum administrations of the combination of AGEN2034; who have achieved a complete response (CR) according to RECIST 1.1; or who have discontinued treatment due to reasons other than disease progression and/or start of a new line of therapy will be in Follow-up for up to approximately 12 months after last dose of study drug or until disease progression and/or start of a new line of therapy. Every effort should be made to collect subject information on the start of new antineoplastic therapy, disease progression and death.

 After the first Follow-up Visit, subjects that present(ed) with progressive disease and/or start new line of therapy will move into Survival Follow-up and should be contacted by telephone every 2 months for up to 12 months after last dose of study drug to assess for survival status. Post-study treatments and the subject's response to them will also be collected.

 Treatment administration and associated procedures for that visit may be delayed for treatment related AEs beyond the window and subsequent schedule adjusted accordingly.

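### Phase 2 follow-up after the last dose is 24 months in some places, but scheduled survival contact stops at 12, and Table 13 contradicts itself on who is followed

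*Protocol*

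**What the plan says.** **Places that give or fit 24 months.**
- Protocol Section 6.3.4: "In Phase 2, subjects who discontinue treatment will be followed for up to 24 months after the last dose of study drug".
- Synopsis, Follow-up Phase: subjects who stop treatment "will be followed for up to 12 months (Phase 1) or 24 months (Phase 2) after the last dose of study drug".
- Synopsis, Planned Trial Duration: the per-subject total includes "a follow-up period of up to 24 months after the last dose of study treatment". Section 3.4 repeats this and gives the total: "The maximum trial duration for a subject is estimated to be up to approximately 49 months".
- Section 3.5: "the end of the trial is defined as 24 months after the last subject has received the last planned dose of study drug". Sections 3.4 and 3.5 do not name Phase 2.

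**Places that stop at 12 months.**
- Section 6.3.4.2: subjects with progression or new therapy are "contacted by telephone to assess for survival status every 2 months for up to 12 months after their last dose of study drug". Section 6.4.1.9.2 repeats the limit.
- Synopsis, Survival Follow-up: they "will be contacted by phone every 2 months to assess for survival for up to 12 months after the last dose of study drug".
- Table 13 footnote 2: they "should be contacted by telephone every 2 months for up to 12 months after last dose of study drug to assess for survival status".
- Section 6.3.4.1: three-monthly visits for subjects without progression or new therapy also end 12 months after the last dose.

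**Who is followed.** Table 13 footnote 1 says that subjects who stop because of progression or new therapy leave the trial after the 3-month visit. Footnote 2 and Sections 6.3.4.1, 6.3.4.2 and 6.4.1.9.1 move the same subjects into survival follow-up.

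**How OS is analyzed.** SAP Section 3.5 lists OS time, median OS and OS rate as secondary endpoints. SAP Section 7.7.10 counts OS from first dose and censors living subjects at last contact. It plans a median with 95% CI, a Kaplan-Meier curve and a listing, and names no time point for the OS rate.

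**The concern.** Section 3.6 refers to Section 6 for survival follow-up, and Section 6 contains both figures, so a site cannot tell how long to keep calling. OS is censored at last contact, so the contact rule largely decides when living subjects leave the risk set. Under the 12-month rule that moment depends on time on drug. If time on drug is related to prognosis, late Kaplan-Meier estimates may be biased. The same may happen if late deaths reach the database while survivors are no longer contacted.

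Footnote 1 is potentially worse. A site that followed it literally would stop collecting survival data after the 3-month visit for subjects who progress, and OS well before month 12 would then suffer. The same sentence stands in Tables 11 and 12, where it fits, because Phase 1 has no survival follow-up.

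**Working it through.** **1. Which follow-up length gives the protocol's own total?** Inputs: screening window of 42 days (Synopsis), treatment of up to 24 months (Section 5.4.1.1), follow-up F.

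Total = 42/30.4375 + 24 + F = 1.38 + 24 + F months.
- F = 24: 49.4, which matches the stated 49.
- F = 12: 37.4, which does not.

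**2. What contact is scheduled after the last dose?**

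| Phase 2 subject | Months 0-12 | Months 12-24 |
|---|---|---|
| Progressed or on new therapy | 3-month visit, then calls every 2 months (footnote 2), or nothing further (footnote 1) | none |
| Neither | visits every 3 months | none |

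Calls and visits are both counted from the last dose, so they cannot be read as 12 months of visits followed by 12 months of calls. Beyond month 12 there is only a general request, without dates, to try to learn of deaths (Table 13 footnote 1, Section 6.3.4.1).

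**3. When does the 12-month rule start to censor?** Let T be the time from first to last dose. The last scheduled contact falls at T + 12 on the OS clock, or T + 11 if two-monthly calls after the 3-month visit fall at months 5, 7, 9 and 11. Since T is at least 0, the rule censors nobody in scheduled contact before about month 12.

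**4. How fast does the risk set thin?** The documents give no figures for time on drug or OS, so these are assumptions: T exponential with median 2, 4 or 6 months, capped at 24; survival after the last dose, S, independent and exponential with median 6 or 10 months; 150 subjects; no data cutoff. With contact for c months after the last dose,

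at risk at t = 150 × P(T + S > t and T + c > t).

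Hand check for medians 2 and 6 at t = 18: the rates are a = ln2/2 and b = ln2/6, so a/(a − b) = 1.5.
- c = 12: 1.5 × 2⁻³ × (2⁻² − 2⁻⁶) + 2⁻⁹ = 0.0459, and × 150 = 6.9.
- c = 24: 1.5 × 2⁻³ × (1 − 2⁻⁶) + 2⁻⁹ = 0.1865, and × 150 = 28.0.

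Simulation of 400,000 subjects gives 7 and 28. The range over the six combinations is:

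| Month | 12-month contact | 24-month contact |
|---|---|---|
| 12 | 55-107 | 55-107 |
| 14 | 27-85 | 44-98 |
| 15 | 19-76 | 39-93 |
| 18 | 7-54 | 28-80 |
| 24 | 1-27 | 14-57 |

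With median treatment of 2 months, 19-29 remain at month 15 and 7-10 at month 18. With 6 months, 45-54 remain at month 18.

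**5. Is there bias, and in which direction?** In the six combinations above, Kaplan-Meier minus truth under 12-month contact is +0.2 to +1.4 points at month 18 and +0.4 to +3.6 at month 24. Three further assumptions, with median T of 3 and median S of 8 months, give at month 24:

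| Assumption | True OS | Kaplan-Meier | Difference |
|---|---|---|---|
| Shorter treatment goes with worse later survival (hazard × 1.5 below median T, × 0.6 above) | 24.2% | 28.5% | +4.3 |
| Unequal post-drug hazards (gamma frailty, variance 1.5), unrelated to T | 33.1% | 28.6% | −4.5 |
| 70% of late deaths reported, survivors not contacted | 19.8% | 13.2% | −6.6 |

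At month 12 the difference is zero in every case. With 24-month contact it is zero through month 24.

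A wider set of assumptions (median time on drug 2.5-4 months; median OS 9-13, or post-drug median 6-10) gave −11.9 to +8.3 points at month 24. Median OS moved by at most 0.2 months (0.3-0.4 if the last call is at month 11). The 95% half-width at month 18 was 6.9-10.7 points against 6.2-8.0 with 24-month contact. In simulated trials of 150 it was 9.8-14.2 against 4.3-7.4 at month 24.

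**6. Does this reach the filing analysis?** From 16 Oct 2019 to the 11 Feb 2021 cutoff (SAP Section 4.2) is 484 days / 30.4375 = 15.9 months. The 61 subjects dosed by 16 Oct 2019 have at least that much potential follow-up, and everyone dosed later has less. At filing the cutoff itself therefore limits most of the tail.

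**The case against.** The case for leaving this alone has several parts.

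- *The 24 months is a ceiling, so 12 months of calls does not breach it.* This stands as a matter of wording. But Section 6.3.4 deliberately separates Phase 1 (12 months) from Phase 2 (24 months), and no procedure stands behind the difference.
- *The planned OS outputs are hardly touched.* This largely stands. The SAP plans a median and a curve, and OS is descriptive in a phase without formal testing (SAP Section 7.1). An OS rate is nevertheless a named endpoint with no time point, whereas duration of response has fixed landmarks (SAP Section 7.7.3), so a late rate is not excluded.
- *The sizes are assumptions.* This stands. Even the sign of the bias depends on the scenario.
- *Censoring is at last contact, not at the last scheduled call.* This stands in part. Unscheduled information can extend follow-up, but it may capture deaths more readily than survivors.

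A reader might infer that OS after about month 12 rests on few subjects. The documents do not support that: the 12 months run from the last dose and OS from the first, and 27-85 of 150 remain at risk at month 14 under the assumptions above. Nor does it follow that OS rates beyond month 12 should be barred.

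**Conclusion.** The protocol is internally inconsistent and wrong as written on two counts: the length of Phase 2 survival contact, and whether progressing subjects are followed at all.

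The statistical consequence of the 12-month rule is real but narrow. The risk set thins once 12 months plus time on drug has passed, markedly from about months 15-18 if treatment is short, which is an assumption. The effect falls mainly on the tail of the curve and on any late OS rate at the final analysis (SAP Section 4.3). Those estimates lose precision and may be biased in either direction. ORR, OS to month 12 and a median reached by about then are essentially unaffected.

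Footnote 1 could reach earlier OS, but only at sites that followed it instead of footnote 2. The documents do not say whether any did.

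**What to change.** **Protocol.** Reconcile the Synopsis, Sections 3.4, 3.5, 6.3.4, 6.3.4.1, 6.3.4.2 and 6.4.1.9.2, and Table 13 to one survival-contact duration for Phase 2. State whether it also covers subjects without progression. A duration of 24 months agrees with the Synopsis follow-up and duration entries and with Sections 3.4, 3.5 and 6.3.4. If 12 months was intended, correct those places instead. Either way, remove from Table 13 footnote 1 the statement that subjects with progression or new therapy leave the trial.

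**SAP Section 7.7.10.** Name the time point or points for the OS rate and report the number at risk at each. Require a vital-status update at data cutoff for every subject not known to be dead, so that deaths and survivors are captured alike. Late OS rates need not be excluded.

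**Cost.** One protocol amendment (Section 10.1) across about 60 centers, about two SAP sentences and, if 24 months is chosen, about six more calls per surviving subject (12 further months at one call every 2 months). Contacts not made on time may not be fully recoverable later.

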### **6.4. Trial Procedures**

The schedules of events in [Section 6.1](#) and [Section 6.2](#) summarize the trial procedures to be performed at each visit in Phase 1 and 2, respectively. Individual trial procedures are described in detail below. It may be necessary to perform these procedures at unscheduled time points if deemed clinically necessary by the investigator.

Furthermore, additional evaluations/testing may be deemed necessary by the investigator and or the Sponsor for reasons related to subject safety. In these cases, such evaluations/testing will be performed in accordance with clinical judgement.

#### **6.4.1. Administrative Procedures**

##### **6.4.1.1. Informed Consent**

The investigator or qualified designee must obtain documented consent from each potential subject prior to participating in the clinical trial and for optional pharmacogenomics research.

##### **6.4.1.2. General Informed Consent**

Consent must be documented by the subject's dated signature along with the dated signature of the person conducting the consent discussion. A copy of the signed and dated consent form should be given to the subject before participation in the trial.

The investigator is responsible for ensuring that a careful and thorough informed consent procedure is implemented before a subject enters the study and at any time during the study should ICF changes be introduced. This includes, but is not limited to: (1) allowing ample time

for this review by the subject; (2) ensuring that qualified medical personnel are available to directly answer questions that a subject may have; (3) ensuring that each potential study subject understands that his or her medical treatment will not be otherwise affected based on the decision whether or not to participate in the study, that his or her participation is completely voluntary, and that he or she can opt to stop participation in the study at any time for any reason; and (4) ensuring a full copy of the signed ICF is given to the subject to take home for his or her medical records. The process for obtaining informed consent should also be noted in the subject's source documentation.

The initial informed consent form, any subsequent revised written informed consent form, and any written information provided to the subject must receive the IRB/ERC's approval/favorable opinion in advance of use. The subject should be informed in a timely manner if new information becomes available that may be relevant to the subject's willingness to continue participation in the trial. The communication of this information will be provided and documented via a revised consent form or addendum to the original consent form that captures the subject's dated signature or by the subject's legally acceptable representative's dated signature.

The informed consent will adhere to IRB/ERC requirements, applicable laws and regulations and Sponsor requirements.

